**Table 2: Management of Rash Events by Severity Grade**

	Definition	Study Drug Action	Activities by Daya	Referral to Dermatologist and Dermatology Activities
Grade 2 rash (with or without pruritus)b	Diffuse, maculopapular rash, or dry desquamation	Study drug intake may be continued at the investigator's discretion	
Day 0: required on-site visit (if a visit is not possible, telephone contact with the subject should take place to collect information and give advice on the necessary measures to be taken).
 
Safety laboratory assessments may be performed at the investigator's discretion (recommended).
 
Determine if subject was adhering to the recommended sun-protective measures. If appropriate, provide sun protection counseling.
 
Day 1 and thereafter: appropriate follow-up visits at the investigator's discretion until resolution of rash or until clinical stability is reached.
 
Safety laboratory assessments are required on Day 1 and are required thereafter only if the previous values were abnormal (but may be performed at the investigator's discretion). If the rash progresses to a higher grade, safety laboratory assessments of the higher grade should be followed.
	
Referral to dermatologist at the discretion of the investigatorc
 
Biopsy not required, but may be performed at the dermatologist's discretion

a)

**Table 2: Management of Rash Events by Severity Grade**

	Definition	Study Drug Action	Activities by Daya	Referral to Dermatologist and Dermatology Activities
Grade 3 rashb	
Vesication, moist desquamation, or ulceration OR
 
Any cutaneous event with 1 of the following:
 
 
- Elevations in AST/ALT <math>>2\times</math>baseline value
 
- Fever <math>>38^{\circ}\text{C}</math> or <math>100^{\circ}\text{F}</math>
 
- Eosinophils <math>>1.00\times 10^3/\mu\text{L}</math>
 
- Serum sickness-like reaction
 
	
Must permanently discontinue JNJ-56136379; no rechallenge allowed
 
NA treatment may be discontinued based on investigator judgement in consultation with the sponsor
	
Day 0: required on-site visit.
 
Safety laboratory assessments required to be performed.
 
Determine if subject was adhering to the recommended sun-protective measures. If appropriate, provide sun protection counseling.
 
Day 1: required on-site visit.
 
Safety laboratory assessments required to be performed.
 
Further visit(s): appropriate follow-up required until resolution of rash or until clinical stability is reached.
 
Safety laboratory assessments are recommended to be performed until the rash severity resolves to Grade 2 or Grade 1.
	
Requiredc
 
Biopsy not required, but may be performed at the dermatologist's discretion.

a)

**Table 2: Management of Rash Events by Severity Grade**

	Definition	Study Drug Action	Activities by Daya	Referral to Dermatologist and Dermatology Activities
Grade 4 rash	Exfoliative dermatitis OR Mucous membrane involvement in at least 2 distinct sites OR Erythema multiforme major OR Stevens-Johnson syndrome OR Toxic epidermal necrolysis OR Necrosis requiring surgery	Must permanently discontinue JNJ-56136379; no rechallenge allowed NA treatment may be discontinued based on investigator judgement in consultation with the sponsor	Day 0 : required on-site visit. Safety laboratory assessments required to be performed. Determine if subject was adhering to the recommended sun-protective measures. If appropriate, provide sun protection counseling. Day 1 : required on-site visit. Safety laboratory assessments required to be performed. Further visit(s) : appropriate follow-up required until resolution of rash or until clinical stability is reached.	Required c Biopsy required and to be performed as soon as possible after the onset of the rash. Safety laboratory assessments are recommended to be performed until the rash severity resolves to Grade 2 or Grade 1.

AE: adverse event; ALT: alanine aminotransferase; AST: aspartate aminotransferase.

a Day 0 of the rash is the first day of investigator assessment and not the first day of rash as reported by the subject. The initial visit should be conducted as soon as possible after the subject contacts the investigator to report the AE (ie, preferably on Day 0). The initial visit and subsequent visits to manage the rash may require unscheduled visit(s).

b The subject should be advised to contact the investigator immediately if there is any worsening of the rash, if any systemic signs or symptoms appear, or if mucosal involvement develops. In case the rash evolves to a higher grade than that first observed, management of the rash should follow the guidelines indicated for the higher grade.

c If applicable, dermatologist visit should occur preferably within 24 hours after onset of rash.

**Notes:**

- a) Local laboratory assessments are to be used for rash management. The values of the local laboratory assessments need to be transcribed in the eCRF by the study site personnel.
- b) A copy of the dermatologist's report, and biopsy if performed, should be made anonymous and will be collected by the monitor.

---

When safety blood samples are drawn as per the rash management guidelines, these should be processed by the local laboratory. The following parameters will need to be tested: AST, ALT, sedimentation rate, complete blood cell count (including hemoglobin, hematocrit, RBC count, WBC count, differential count [neutrophils, lymphocytes, monocytes, eosinophils, and basophils], and platelet count), and creatinine. The values of the local laboratory assessments need to be transcribed in the eCRF by the study site personnel.

The subject may be treated symptomatically until the rash resolves. Oral antihistamines (eg, cetirizine, levocetirizine) and/or topical corticosteroids may provide symptomatic relief but effectiveness of these measures has not been established. If systemic corticosteroids for longer than 24 hours are required for treatment of rash, the study drug needs to be permanently discontinued. If the rash is considered to be most likely due to concomitant illness or non-study drugs, standard management, including discontinuation of the likely causative agent, should be undertaken.

## **Health Questionnaire**

**English version for the USA**

*USA (English) © 2009 EuroQol Group. EQ-5D™ is a trade mark of the EuroQol Group*

## APPENDIX 11: 5-LEVEL EUROQOL 5-DIMENSION QUESTIONNAIRE (EQ-5D-5L)

 EQ-5D-5L		
EQ-5D-5L Tablet version		Country (Language)
English (USA)		Health Questionnaire
Health Questionnaire		Version (Target Language)
English version for the USA		Version (English)
Please tap the ONE box that best describes your health TODAY.		Instruction
MOBILITY		Mobility
I have no problems walking		MB1
I have slight problems walking		MB2
I have moderate problems walking		MB3
I have severe problems walking		MB4
I am unable to walk		MB5
SELF-CARE		Self-care
I have no problems washing or dressing myself		SC1
I have slight problems washing or dressing myself		SC2
I have moderate problems washing or dressing myself		SC3
I have severe problems washing or dressing myself		SC4
I am unable to wash or dress myself		SC5
USUAL ACTIVITIES (e.g. work, study, housework, family or leisure activities)		Usual Activities
I have no problems doing my usual activities		UA1
I have slight problems doing my usual activities		UA2
I have moderate problems doing my usual activities		UA3
I have severe problems doing my usual activities		UA4
I am unable to do my usual activities		UA5
PAIN / DISCOMFORT		Pain / Discomfort
I have no pain or discomfort		PD1
I have slight pain or discomfort		PD2
I have moderate pain or discomfort		PD3
I have severe pain or discomfort		PD4
I have extreme pain or discomfort		PD5
ANXIETY / DEPRESSION		Anxiety / Depression
I am not anxious or depressed		AD1
I am slightly anxious or depressed		AD2
I am moderately anxious or depressed		AD3
I am severely anxious or depressed		AD4
I am extremely anxious or depressed		AD5
We would like to know how good or bad your health is TODAY.		Vas Line 1
This scale is numbered from 0 to 100.		Vas Line 2
100 means the best health you can imagine.		Vas Line 3
0 means the worst health you can imagine.		Vas Line 4
Please tap on the scale to indicate how your health is TODAY.		Vas Line 5
The best health you can imagine		Top Scale
The worst health you can imagine		Bottom Scale
YOUR HEALTH TODAY		Box Health
Next		button.next
Previous		button.previous
© EuroQol Research Foundation. EQ-5D™ is a trade mark of the EuroQol Research Foundation		
Disclaimer: This is a preview of the EQ-5D instrument. It demonstrates the text, questions and response options included in this version. This preview does not represent the final product and should not be used as an official EQ-5D instrument.		

---

## APPENDIX 12: HEPATITIS B QUALITY OF LIFE INSTRUMENT (HBQOL)

### HBQOL v1.0 QUESTIONNAIRE

**Some people with hepatitis B say that having hepatitis B affects the way they feel socially and mentally.**

**Below is a list of statements about how hepatitis B might make you feel socially or mentally. Please read each one carefully and circle the number that best describes how frequently, if ever, you feel that way. Circle only one number for each statement and do not skip any items.**

		Never	Rarely	Sometimes	A Lot of the Time	All of the Time
F1	I feel ashamed because of hepatitis B	1	2	3	4	5
F2	I feel stigmatized because of hepatitis B	1	2	3	4	5
F3	I feel sad because of hepatitis B	1	2	3	4	5
F4	I feel frustrated because of hepatitis B	1	2	3	4	5
F5	I feel worn out and tired because of hepatitis B	1	2	3	4	5
F6	I feel anxious because of hepatitis B	1	2	3	4	5
F7	I feel angry because of hepatitis B	1	2	3	4	5
F8	I feel isolated from others because of hepatitis B	1	2	3	4	5
F9	I feel like something bad might happen because of hepatitis B	1	2	3	4	5
F10	I feel my life is less enjoyable because of hepatitis B	1	2	3	4	5
F11	I feel like sexual activity is difficult for me because of hepatitis B	1	2	3	4	5
F12	I feel like I am less productive because of hepatitis B	1	2	3	4	5
F13	I feel scared because of hepatitis B	1	2	3	4	5

**CONTINUE TO NEXT PAGE →**

---

**Some people have concerns about their hepatitis B.**

Below there is a list of possible concerns that some people have expressed about hepatitis B. For each one, please think about whether you also have that concern and, if so, how much of a concern it is to you. Circle the number that best describes your level of concern for each statement. Circle only one number for each statement and do not skip any items.

	How concerned are you that...	Not at All Concerned	A Little Bit Concerned	Moderately Concerned	Quite a Bit Concerned	Extremely Concerned
C1	One day you could develop liver failure because of your hepatitis B	1	2	3	4	5
C2	You might develop liver cancer because of your hepatitis B	1	2	3	4	5
C3	Someone influential, like your boss, might find out about your hepatitis B	1	2	3	4	5
C4	You could transmit hepatitis B to a child	1	2	3	4	5
C5	Your hepatitis B may flare up at any time	1	2	3	4	5
C6	It is easier to get other illnesses because of having hepatitis B	1	2	3	4	5
C7	You could transmit hepatitis B to a partner through sex	1	2	3	4	5
C8	You have to watch what medicines you take because you have hepatitis B	1	2	3	4	5
C9	Hepatitis B might affect your life expectancy	1	2	3	4	5
C10	You are overly self-conscious because of hepatitis B	1	2	3	4	5

**CONTINUE TO NEXT PAGE →**

	How concerned are you that...	Not at All Concerned	A Little Bit Concerned	Moderately Concerned	Quite a Bit Concerned	Extremely Concerned
C11	You could be socially isolated because of hepatitis B	1	2	3	4	5
C12	Something serious might be wrong because of your hepatitis B	1	2	3	4	5
C13	You have to watch what you eat because you have hepatitis B	1	2	3	4	5
C14	You might be embarrassed because of your hepatitis B	1	2	3	4	5
C15	Your health might unexpectedly get worse because of hepatitis B	1	2	3	4	5

**CONTINUE TO NEXT PAGE →**

**Some people with hepatitis B say that having hepatitis B affects the way they feel physically.**

**Below is a list of physical symptoms. Please read each one carefully and circle the number that best describes how frequently, if ever, you think that hepatitis B (as opposed to other conditions) causes that symptom.**

	How frequently do you feel...	Never	Rarely	Sometimes	A Lot of the Time	All of the Time
P1	Tiredness	1	2	3	4	5
P2	Memory problems	1	2	3	4	5
P3	Muscle aches	1	2	3	4	5

**\*\* END OF QUESTIONNAIRE \*\***

Thank you for your time and effort in answering these questions. Please check over your responses to make sure you did not skip any questions.

---

## **Scaling and Scoring Instructions**

There are 31 scored items included in the HB-QOL, including 13 items regarding how HBV makes patients feel socially or mentally (F1-F13), 15 items regarding HBV-related concerns (C1-C15), and 3 items regarding HBV-related physical impacts.

Each item is scored on a 5-level response scale ranging from 1 through 5. Each response is transformed along a 0 to 100-point scale, where lower scores denote less HRQOL impact, and higher scores denote more HRQOL impact (i.e. 0=best score; 100=worst score), as follows:

**Level 1 – 0 points**

**Level 2 – 25 points**

**Level 3 – 50 points**

**Level 4 – 75 points**

**Level 5 – 100 points**

The items are combined to form 7 subscales, as follows:

### **Psychological Well-Being (8 Items)**

Anxious (F6)

Frustrated (F4)

Sad (F3)

Angry (F7)

Less Enjoyable (F10)

Scared (F13)

Bad (F19)

Isolated (F8)

### **Anticipation Anxiety (6 Items)**

Concern Failure (C1)

Concern Cancer (C2)

Concern Worsen (C15)

Concern Serious (C12)

Concern Survival (C9)

Concern Flare (C5)

### **Vitality (5 Items)**

Tiredness (P1)

Worn Out (F5)

Muscle Aches (P3)

Memory Problems (P2)

Unproductive (F13)

---

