**The items are combined to form 7 subscales, as follows:**

Psychological Well-Being (8 Items), Anticipation Anxiety (6 Items), Vitality (5 Items), Stigma (6 Items), Vulnerability (3 Items), Transmission (3 Items) and Viral Response (4 Items).

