**The global score that reflects the results on all 31 items.**

Each subscale score is simply calculated as the average score among the items included in that subscale. The global score is simply the average score among all the items in the HBQOL.

For example, consider these sample scores for items in the vulnerability scale:

Item Number	Item Name	Raw Score	Scaled Score
C13	Concern eat	2	25
C6	Concern sick easily	4	75
C8	Concern medicines	3	50
		Average	50

The score on this subscale is 50 out of a possible score of 100, where higher scores denote more severe negative impact of HBV on HRQOL. The scores will be derived if at least 50% of the items or domain scores are available respectively, no imputation of missing data will be performed.

---

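### Two item codes in the HBQOL scoring key contradict the questionnaire, so Vitality and Psychological Well-Being would be mis-scored if programmed from the codes rather than the labels

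*SAP*

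**What the plan says.** SAP Section 8.2 describes HBQOL scoring. Each of 31 items is rescaled to 0–100. The section names seven subscales and gives their sizes as 8, 6, 5, 6, 3, 3 and 4 items, with Psychological Well-Being the 8-item scale and Vitality the 5-item one. The rule is "Each subscale score is simply calculated as the average score among the items included in that subscale", and on missing items: "The scores will be derived if at least 50% of the items or domain scores are available respectively". Section 8.2 does not say which items belong to which subscale. That map appears only in the scoring instructions at the end of SAP Appendix 12 and, identically, in protocol Attachment 5.

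Those instructions state the numbering: "There are 31 scored items included in the HB-QOL, including 13 items regarding how HBV makes patients feel socially or mentally (F1-F13". The questionnaire in the same appendix agrees with it. Three of its items matter here:

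- F9: "I feel like something bad might happen because of hepatitis B"
- F12: "I feel like I am less productive because of hepatitis B"
- F13: "I feel scared because of hepatitis B"

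The Vitality list in the key ends with "Unproductive (F13". The Psychological Well-Being list contains *Scared* coded F13, which is right, and *Bad* coded F19.

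**The concern.** A scoring key is what a programmer turns into code. In these two entries the label and the code disagree, and the plan does not say which governs. Followed by code, one fifth of Vitality becomes a fear item in place of the productivity item, and Psychological Well-Being asks for an item that is not on the form.

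The Vitality error would be the harder one to notice. F13 is a real, answered item, so the subscale still has five populated entries and nothing fails. Comparing the SAP key with the protocol key would not help, because both carry the same two codes.

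The subscales are used. SAP Section 8.5.2 plans descriptive statistics and change from baseline for the derived scores, a tabulation of HBQOL by dimension, and a repeated-measures model giving treatment-group means and effect sizes. HBQOL is also the only hepatitis B-specific instrument among the four patient-reported outcomes.

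**Working it through.** **Inputs.** The questionnaire codes are F1–F13, C1–C15 and P1–P3 (SAP Appendix 12). The item lists come from the key in the same appendix, and the stated sizes from SAP Section 8.2.

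**What reproduces.**
- Item count: 13 + 15 + 3 = 31, as stated.
- Entries listed in the key: 8 + 6 + 5 + 6 + 3 + 3 + 4 = 35, each subscale matching its stated size.
- Worked Vulnerability example: (25 + 75 + 50)/3 = 50, as stated.

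**What does not: the codes.** Five codes appear twice in the key: C4, C7, C8 and C13 (Viral Response shares them with Transmission and Vulnerability) and F13 (Psychological Well-Being and Vitality). That leaves 35 − 5 = 30 distinct codes. One of them, F19, does not exist, so 29 of the 31 items reach a subscale. The two left out are F9 and F12.

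**With *Bad* read as F9 and *Unproductive* as F12.** The sizes stay 8/6/5/6/3/3/4. The only repeats are C4, C7, C8 and C13, so there are 35 − 4 = 31 distinct codes. All are valid and every item is covered. The labels and the count point to the same correction.

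**Size of the error if scored by code, all items answered.**

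*Vitality.* Four items (P1, P2, P3, F5) are the same either way, so

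error = (F13 − F12)/5.

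One response level is 25 points, giving 25/5 = 5 points per level of difference. The maximum is 100/5 = 20 points. For example, with P1, P2, P3 and F5 all at 25, F12 at 100 and F13 at 0, the intended score is (4 × 25 + 100)/5 = 40 and the score by code is (4 × 25 + 0)/5 = 20. A subject who answers F12 and F13 alike has no error.

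*Psychological Well-Being.* If F19 is treated as missing, the score is the mean M of the other seven items instead of (7M + F9)/8, so

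error = M − (7M + F9)/8 = (M − F9)/8.

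The maximum is 100/8 = 12.5 points. Seven of eight items is 87.5%, above the 50% threshold, so the score would still be produced unless the item count is checked.

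*Everything else.* The other five subscales contain neither wrong code. The global score averages all 31 items directly and does not use the key's lists.

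**The case against.** The strongest reply is that the labels leave no doubt. *Unproductive* can only be F12, *Bad* can only be F9, and *Scared* is listed separately with its right code. Anyone reading the labels scores correctly, and checking the key against the questionnaire in the same appendix exposes both errors. Item responses are held individually, so a mis-scored subscale could be recomputed. HBQOL is exploratory, SAP Section 8.5.2 gives it no threshold for important change, and no treatment, stopping or efficacy decision depends on it. All of this stands. It makes the harm conditional and the severity low, but it does not reconcile the key with the questionnaire.

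A reader might infer more than the documents support:

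- *That Vitality will be mis-scored.* This holds only if the program follows the codes, and the documents do not say that it does.
- *That the 50% rule would hide the lost item.* The rule concerns unanswered items. A reference to a field not on the form, or a count of 7 against a heading of 8, may well be caught.
- *That study programmers are known to do the scoring.* SAP Sections 8.3 and 8.4 name a vendor for the other two multi-item scales and Section 8.2 names nobody. In-house scoring is a fair inference, not a statement.
- *That neither subscale would measure what it is named for.* Psychological Well-Being would lose one item and gain none; only Vitality takes in a foreign item, at one fifth weight.
- *That the fear item would drift with open-label allocation or virological results.* Nothing in the documents shows F13 behaving differently from F12.

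**Conclusion.** The two codes are wrong on the face of both documents, and the appendix key is the only item map for subscales that are to be tabulated and modelled. Under scoring by code, Vitality is off by 5 points per response level between F13 and F12, at most 20; Psychological Well-Being is off by at most 12.5; and F9 and F12 count in no subscale. These are limits for a single subject with every item answered. No shift in group means can be estimated from the documents, and under scoring by label the error is nil. The global score, the other five subscales and the primary endpoint are untouched. Minor severity: worth correcting because the plan should not leave the choice between label and code to chance. That F9 and F12 are the intended items rests on the labels and the coverage check; the instrument's scoring manual is not among the documents.

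**What to change.** Confirm the two items against the instrument's scoring manual. Then, in SAP Appendix 12 and protocol Attachment 5, change the code for *Bad* from F19 to F9 and the code for *Unproductive* from F13 to F12. In SAP Section 8.2, state that subscales are programmed from the corrected key, with a check that every one of the 31 items appears in at least one subscale and that the sizes are 8/6/5/6/3/3/4. Both parts of the check need to use valid questionnaire codes: the sizes alone already agree with the uncorrected key, while the coverage part flags F9 and F12. The cost is two codes in each document and a few lines of program; no new data are needed, and any subscale already scored from the codes can be recalculated from the item responses.

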### **Stigma (6 Items)**

Concern Embarrassed (C14)  
Ashamed (F1)  
Concern Self-Conscious (C10)  
Concern Socially Isolated (C11)  
Concern Boss (C3)  
Stigmatized (F2)

### **Vulnerability (3 Items)**

Concern Eat (C13)  
Concern Sick Easily (C6)  
Concern Medicines (C8)

### **Transmission (3 Items)**

Concern Transmit Sex (C7)  
Concern Transmit Child (C4)  
Sex Difficult (F11)

### **Viral Response (4 Items)**

Concern Transmit Sex (C7)  
Concern Transmit Child (C4)  
Concern Eat (C13)  
Concern Medicines (C8)

In addition, there is a single **global score** that reflects the results on all 31 items.

Each subscale score is simply calculated as the average score among the items included in that subscale. The global score is simply the average score among all the items in the HBQOL.

For example, consider these sample scores for items in the vulnerability scale:

Item Number	Item Name	Raw Score	Scaled Score
C13	Concern eat	2	25
C6	Concern sick easily	4	75
C8	Concern medicines	3	50
		Average	50

The score on this subscale is 50 out of a possible score of 100, where higher scores denote more severe negative impact of HBV on HRQOL.

**APPENDIX 13: MEDICAL OUTCOMES STUDY COGNITIVE FUNCTIONING SCALE-REVISED (MOS-CFS COG-R)**

Translation Copyright © 2010, 2012  
QualityMetric Incorporated.

All rights reserved.

(United Kingdom (English) MOS 6-Item Cognitive Functioning Scale  
Single-Item Presentation Text-Revised)

